Two cases of positive Diaskintest with normal chest X-ray were recorded during the study. It should be noted that no active tuberculosis infection was recorded in the study subjects with positive Diaskintest results during the study. Special attention should be paid to AE “esophagus candidiasis” recorded in one patient (1.23%). Candida infections of various localization, in particular, esophagus, have been described for interleukin-17 blockers. These events are classified as adverse events of special interest. In the extension study, esophagus candidiasis was of grade 2 and resolved without sequelae after a medication therapy.

If considering the route of administration (SC injections), injection site reactions are expected for BCD-085. The proportion of patients with injection site reactions was 1.23% (one patient had two local reactions, which included hyperemia, swelling, itch, pain and local infiltrate). This shows a low incidence rate of this AE.

To assess the risk of increasing AE/SAE rate during the long-term use of BCD-085, exposure-adjusted AEs incidence rate (EAIR) was assessed during the extension phase and compared with that during the BCD-085-3 study. The EAIR for the BCD-085-3 study was 1.379, for the BCD-085-3ext – 0.588. Thus, the frequency of AE/SAE showed a tendency towards a decrease during the long-term use, suggesting no risk of AE rate increase over time.

The immunogenicity assessment did not detect binding anti-BCD-085 antibodies in any patient.

Thus, the obtained data confirmed the high efficacy of BCD-085 (JSC BIOCADC, Russia) in ankylosing spondylitis. The response was stable over time; it was more frequent with BCD-085 120 mg. The safety profile of BCD-085 was favorable.

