**Immunogenicity:**

- Proportion of patients with anti-drug antibodies (binding/neutralizing)

will be processed using the frequency tables, Fisher's test,  $\chi^2$  test, and Cochran-Mantel-Haenszel test. The categorical data will be described using percentages or proportions.

For multiple comparisons, the Benjamini-Yekutieli procedure will be used. Regression will be used to assess the effects of the factors other than the therapy type. Time to loss of response will be assessed using log-rank test, Kaplan-Meier curves, and Cox regression model. Time will be counted from the response during the treatment with BCD-085. Right censoring can be used to analyze time to events.

Statistical methods will be chosen based on the type and distribution of raw data. Applicability of certain statistical tests will be evaluated after all the data are collected because it is impossible to predict the distribution pattern, data homogeneity and other data characteristics in advance.

The data will be processed using programming language R for statistical processing and SAS 9.4 software environment.

Translated from Russian to English, dated 26-Nov-2019

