The following categorical data will be analyzed in the study:

Efficacy:

- Proportion of patients with PASI 75/90/100,
- Proportion of patients with sPGA score 0 or 1,
- Proportion of patients with DLQI score 0 or 1,
- Proportion of patients (among patients with psoriatic arthritis) who achieved an ACR20/50/70,
- Proportion of patients who maintained PASI 75/90/100 score,
- Proportion of patients who maintained sPGA score 0 or 1,

- Proportion of patients who maintained DLQI score 0 or 1,
- Proportion of patients who maintained ACR 20/50/70 response (among patients with psoriatic arthritis).

Safety:

- Proportion of patients who developed AEs/SAEs,
- Proportion of patients who developed injection site reactions,
- Proportion of patients who developed Grade 3/4 AEs/SAEs,
- Proportion of patients who discontinued the study due to AEs and/or SAEs,
- Exposure adjusted incidence rate of AEs/SAEs during the extension study.

Immunogenicity:

- Proportion of patients with anti-drug antibodies (binding/neutralizing).

Demographics and other baseline characteristics:

- General information (Race, Sex, Childbearing potential (women)),
- Prior therapies for plaque psoriasis,
- Co-morbidities and the most relevant prior diseases,
- Medical history.

Extent of exposure:

- The number of administrations given during the study,
- Exposure of BCD-085 with mean daily dose and treatment duration.

Percentages or proportions will be used to describe categorical data.

Categorical data will be processed using frequency tables, the Fisher's exact test, Yates-corrected Pearson's χ^2 test, and the Cochran-Mantel-Haenszel test.

The Benjamini-Yekutieli correction for multiple testing will be used.

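### The extension's exposure-adjusted AE rate is filed as categorical data, for which the plan gives only proportions and contingency-table tests; it needs a person-time definition and a rate method

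*SAP*

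**What the plan says.** SAP 8.2 opens its list with "The following categorical data will be analyzed in the study". Under Safety, that list includes "Exposure adjusted incidence rate of AEs/SAEs during the extension study", next to the proportion of patients with AEs/SAEs. Two sentences then cover every item: "Percentages or proportions will be used to describe categorical data", and "Categorical data will be processed using frequency tables, the Fisher's exact test", followed by Yates-corrected chi-square and Cochran-Mantel-Haenszel.

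Protocol 9.1 puts the same rate in its categorical safety list and states that the listed items "will be processed using the frequency tables, Fisher's test", chi-square and Cochran-Mantel-Haenszel.

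Neither document gives the rate a numerator, a person-time denominator, a unit or a confidence interval, and neither names a method for rates. SAP 9 plans no additional analyses, and SAP 10 declares no departure from the protocol's methods.

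**The concern.** An exposure-adjusted rate divides patients or events by time at risk. It has no upper limit of 1 and does not arise from a table of patient counts. The plan's descriptive method and tests all work on patient counts, so there is no valid way to apply them to this variable.

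The only literal application is to count patients with at least one AE and ignore time. That duplicates an endpoint already in the same list and removes the one thing the rate adds. Exposure is unequal here by design, because Arm 3 has a longer extension to make up for its 12 placebo weeks, and dropout will add to the inequality. Evaluating long-term safety is a stated objective of the extension. In the ankylosing spondylitis programme (Protocol 1.3.2.2.4) the sponsor used this same measure to argue that AE frequency does not rise with longer use.

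**Working it through.** **1. Is the sponsor's measure a person-time rate?** Protocol 1.3.2.2.4 states "The EAIR for the BCD-085-3 study was 1.379" and gives 0.588 for the extension study BCD-085-3ext. A value of 1.379 exceeds 1 and cannot be a proportion of patients.

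The 0.588 can be rebuilt from the same section: 81 patients, 33 with at least one AE, dosing through Week 36 of the extension. Assuming full 36-week exposure for everyone:

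33 / (81 × 36/52) = 33 / 56.08 = 0.588 per patient-year.

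With 40 weeks it would be 0.530. The match supports reading the measure as patients with an AE per patient-year. The 1.379 does not reproduce from the printed counts with 12-week exposure: 27/(88 × 12/52) = 1.330 for all patients, and 20/(66 × 12/52) = 1.313 for the active arms. The numerator or the exposure convention is therefore not fully recoverable from the documents, which is a further reason to define both.

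**2. How unequal is exposure?** From SAP 3.1 and SAP 5:

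- Full extension: 154 − 54 = 100 weeks in Arms 1 and 2; 166 − 54 = 112 weeks in Arm 3; ratio 1.12.
- Supplementary Report 2 cut-off: 110 − 54 = 56 weeks; 122 − 54 = 68 weeks; ratio 1.21.

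The four-week follow-up is listed as a separate period and is not counted here.

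**3. What would a proportion show if the true rates were equal?** Assume a constant hazard λ per year, the same in every arm, with complete follow-up: P(at least one AE) = 1 − exp(−λ × weeks/52.18).

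| λ per year | 100 weeks | 112 weeks | gap (points) | 56 weeks | 68 weeks | gap (points) |
|---|---|---|---|---|---|---|
| 0.2 | 31.8% | 34.9% | 3.1 | 19.3% | 22.9% | 3.6 |
| 0.588 | 67.6% | 71.7% | 4.1 | 46.8% | 53.5% | 6.7 |
| 1.0 | 85.3% | 88.3% | 3.0 | 65.8% | 72.8% | 7.0 |

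On the person-time scale the rate ratio is 1.00 in every row.

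**4. Is 0.588 a fair hazard?** Only approximately. It divides by total exposure, not by time to first event. A hazard of 0.588 over 36 weeks gives 1 − exp(−0.588 × 36/52) = 33.4%, whereas 33/81 = 40.7% was observed. The hazard that matches is −ln(1 − 33/81)/(36/52) = 0.76 per year. It gives 76.5% and 80.3% over the full extension (gap 3.8 points) and 55.6% and 62.7% at Report 2 (gap 7.1 points). The gaps hardly move.

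**5. Would a test pick it up?** The number entering the extension is not stated, because only Week 52 PASI 75 responders continue. Taking the maximum of 170 (Arms 1 and 2) and 43 (Arm 3), the standard error of the difference at λ = 0.588 over the full extension is √(0.676 × 0.324/170 + 0.717 × 0.283/43) = 7.8 points, against a gap of 4.1. At Report 2 it is √(0.468 × 0.532/170 + 0.535 × 0.465/43) = 8.5 points, against 6.7. For the full extension, exact rejection probabilities at two-sided 0.05 under equal rates, for hazards from 0.2 to 1.379, are at most 0.065 for Fisher and 0.051 for Yates. With 120 and 30 patients, Fisher stays at about 0.05 or below. Rejection probabilities were not worked out for Report 2.

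**The case against.** The best defence is that this is a misfiled line, not a chosen method. The tests are a general set for a mixed list, which also contains "Exposure of BCD-085 with mean daily dose and treatment duration", equally not categorical. Protocol 9.1 adds that methods will follow the type and distribution of the data and that applicability will be judged once the data are in. The sponsor's earlier practice was to report the measure as a rate with no test, and 0.588 reproduces with a person-time denominator. The crude proportion is already an endpoint, so nobody has reason to compute it twice.

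Most of this is fair as a forecast of what the sponsor will do. It does not repair the text. The protocol clause names no rate method and defers the choice until after data collection. The SAP, where the choice should be settled, repeats the classification and adds nothing.

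Two stronger readings are tempting. The first is that the plan will produce a false safety difference between arms. The documents do not support this. The comparative safety objective (Q4W against Q2W) belongs to the main period; all arms receive the same regimen in the extension; and SAP 5 mentions analysis by study arm for the Final Report and Supplementary Report 1, but not for Reports 2 and 3. The second is that the plan overlooks Arm 3's longer extension. It does not: the SAP sets out the extra 12 weeks and uses arm-specific cut-offs, and a rate computed with person-time would account for them. Only the assigned proportions and tests would not.

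**Conclusion.** The point stands as a mismatch of method and variable, together with a missing definition, in both documents. It rests on the wording of SAP 8.2 and Protocol 9.1 and on the sponsor's own value above 1, and does not depend on the size of any bias.

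The size is modest. Treating the rate as a proportion would open a gap of about 3 to 4 points between arms with equal rates over the full extension, and about 4 to 7 points at the Report 2 cut-off, for hazards from 0.2 to 1.0 per year. Type I error over the full extension would hardly change. These figures assume a constant hazard, complete follow-up and the planned arm sizes, and matter only if arms are set side by side. This is one secondary safety measure in an open-label extension; no confirmatory hypothesis depends on it. It should be corrected because the endpoint as planned cannot be analysed by the methods given for it.

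**What to change.** - Remove the rate from the categorical lists in SAP 8.2 and Protocol 9.1, and move treatment duration and mean daily dose out of the SAP list at the same time.
- Define the rate as patients with a first event divided by patient-years of extension exposure and, separately, as events divided by patient-years. State when time stops for each numerator, how dropouts contribute, and whether the four-week follow-up counts.
- Report both with exact Poisson 95% confidence intervals.
- Only if arms or study periods are compared, use a rate ratio from Poisson or negative-binomial regression with log person-time as offset.

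The cost is a change of wording in two documents and standard output. No new data are needed, because event dates and dosing dates are already collected.

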8.3. The level of significance to be used

The level of significance is set as 0,05 (5%) with statistical power of 0,8 (80%).

8.4. Accounting for missing, unavailable or doubtful data, outliers

Missing, unused, and spurious data will not be substituted.

Spurious and unevaluable data are revealed during the outlier analysis by examination of Mahalanobis or Cook distance, visual analysis of scatter plots and box plots.

All actions taken to handle missing, unevaluable, spurious data and outliers before/during the statistical analysis will be described in the Clinical Study Report.

8.5. Statistical evaluations for the early study termination

Not available.

8.6. Subgroup analysis, interaction and related variables

Not available.

9. OTHER PLANNED ANALYSES

No additional analyses are planned in this study.

10. DEVIATIONS FROM ANALYSIS METHODS DESCRIBED IN STUDY PROTOCOL

This Statistical Analysis Plan has no deviations from methods described in Study Protocol.
